8.7 Statistical Analysis of Pharmacokinetic Parameters

An estimate of the relative systemic exposure after multiple dose administration of YLP-001 using plasma verproside and picroside II AUC_{τ} , AUC_{0-t} , and C_{max_ss} on Day 54 (± 1) or Day 56 will be performed by dose-normalized (to 80 mg YLP-001) ratio analysis (i.e., parameter values for 160 mg versus parameter values for 80 mg; Treatment B Versus Treatment A), expressing the geometric mean ratio (GMR) and 90% confidence interval (CI) of the GMR.

The ANOVA analysis will be performed using the following SAS[®] code:

```
PROC MIXED;  
CLASS TREATMENT SUBJECT;  
MODEL PK_PARAMETER = TREATMENT;  
ESTIMATE "B vs A" TREATMENT -1 1 / cl alpha=0.1 e;  
LSMEANS TREATMENT / cl;
```

Note: Parameters will be dose-normalized to 80 mg YLP-001, prior to analysis.

Additional analyses may be performed as deemed necessary upon review of the data and/or upon Sponsor's request.

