8.2 Bioanalytical Method

Plasma concentrations of verproside and picroside II will be determined using the bioanalytical method SOP (EDT) methods validated with respect to accuracy, precision, linearity, sensitivity, and specificity at Celerion, Lincoln, Nebraska, USA.

The validated analytical range (lower limit of quantitation [LLOQ] – upper limit of quantitation [ULOQ]) for verproside and picroside II is 50.0 – 20 000 pg/mL.

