$t_{1/2}$	$t_{1/2}$	Apparent first-order elimination half-life.	Calculated as: $\ln(2)/k_{el}$
CL/F	CL/F	Apparent total plasma clearance after extravascular administration (verproside only).	Calculated as: $Dose/AUC_{0-\infty}$
V_z/F	V_z/F	Apparent volume of distribution during the terminal elimination phase after extravascular administration (verproside only).	Calculated as: $Dose/(k_{el} \times AUC_{0-\infty})$

Following Multiple Doses of YLP-001 - Day 54 (\pm 1) or Day 56			
Parameter	Label to be Used in Tables	Definition	Method of Determination
AUC _τ	AUCtau	AUC over the final 12-hour dosing interval (τ) at steady state (e.g., 0-12 hours).	Calculated using the Linear Trapezoidal with Linear Interpolation Method. May be extrapolated using the k_{el} , if C_t occurs prior to 12 hours postdose.
AUC _{0-t}	AUC0-t	AUC from time zero to time t , where t is the time of the C_t .	Calculated using the Linear Trapezoidal with Linear Interpolation Method.
C _{max_ss}	Cmax_ss	Maximum observed plasma concentration during a dosing interval at steady state.	Taken directly from bioanalytical data.
C _{min_ss}	Cmin,ss	Minimum observed/measured non-zero concentration during a dosing interval at steady state.	Taken directly from bioanalytical data.
t _{max_ss}	tmax_ss	Time to reach C _{max_ss} (obtained without interpolation).	Observed
C _{trough}	Ctrough	Plasma concentration observed at the end of a dosing interval at steady state. Presented as predose in the morning Days 15 (\pm 2), 29 (\pm 2), 43 (\pm 2), and 54 (\pm 2) (following PM dosing on Days 14 (\pm 2), 28 (\pm 2), 42 (\pm 2), and 54 (\pm 1) or 56, respectively).	Taken directly from bioanalytical data.
C _{avg_ss}	Cavg_ss	Average plasma concentration at steady state.	Calculated as: AUC_{τ}/τ
%Fluc	%Fluc	Percent peak-to-trough fluctuation at steady-state.	Calculated as: $(C_{max_ss} - C_{min_ss})/C_{avg_ss} \times 100$
Swing	Swing	Percent swing at steady-state.	Calculated as: $(C_{max_ss} - C_{min_ss})/C_{min_ss} \times 100$

Following Multiple Doses of YLP-001 - Day 54 (\pm 1) or Day 56			
Parameter	Label to be Used in Tables	Definition	Method of Determination

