k_{el}	kel	Apparent first-order terminal elimination rate constant, which represents the fraction of drug eliminated per unit time.	Calculated from a semi-log plot of the plasma concentration versus time curve, calculated by linear least-squares regression analysis using the maximum number of points in the terminal log linear phase (e.g., three or more non-zero plasma concentrations).
$t_{1/2}$	$t_{1/2}$	Apparent first-order elimination half-life.	Calculated as: $\ln(2)/k_{el}$
CL_{ss}/F	CL_{ss}/F	Total body clearance estimated at steady-state after oral administration (verproside only).	Calculated as: $Dose/AUC_{\tau}$
$R_{A,AUC}$	RA,AUC	Accumulation ratio	Calculated as: AUC_{τ} / AUC_{0-12} (on Day 1) If AUC_{0-12} on Day 1 or AUC_{τ} on Day 54 (\pm 1) or 56 cannot be calculated for a patient, then no $R_{A,AUC}$ value will be presented for that patient.
$V_{z,ss}/F$	$Vz,ss/F$	Apparent volume of distribution at steady state.	Calculated as: $(CL_{ss}/F)/k_{el}$

For the calculation of the PK parameters that depended on the dose (CL/F , V_z/F , CL_{ss}/F , and $V_{z,ss}/F$) verproside content is 28.96 and 57.92 mg for the 80 and 160 mg YPL-001 dose levels, respectively.

Actual sample times will be used in the calculations. Patients for whom there are insufficient data to calculate the PK parameters (at least 3 consecutive measurable concentrations) will be included in the concentration tables only and excluded from the pharmacokinetic and statistical analyses.

For the calculation of the PK parameters, plasma concentrations below the limit of quantitation (BLQ) prior to the first quantifiable concentration will be set to 0.00 and plasma concentrations BLQ after the first quantifiable concentration will be treated as missing.

Plasma verproside and picroside II C_{trough} concentrations will be presented. Although C_{trough} concentrations are related to the PM dose given on Days 14 (\pm 2), 28 (\pm 2), 42 (\pm 2), and 53 (\pm 2), they will be labeled and referred with in the TFLs as AM predose time point on Days 15 (\pm 2), 29 (\pm 2), 43 (\pm 2), and 54 (\pm 1) or Day 56.

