For the calculation of summary statistics and PK parameters, BLQ plasma concentrations will generally be set to 0 prior to the first quantifiable concentration on each study day and to missing thereafter. Based on the reported mean $t_{1/2}$ of plasma verproside and picroside II following the BID administration of 80 mg YPL-001 in a previous multiple ascending dose (MAD) study in healthy subjects, C_{trough} that are BLQ may be expected in this study. Therefore, C_{trough} BLQ concentrations measured at predose on Days 15 (± 2), 29 (± 2), 43 (± 2), and 54 (± 1) or Day 56 will be set to 0 for the calculations of summary statistics and PK parameters.

The k_{el} will be determined using linear regressions composed of least 3 data points. The k_{el} will not be assigned if 1) the terminal elimination phase is not apparent, 2) if t_{max} is one of the 3 last data points, or 3) if the R^2 value is less than 0.8. For the analysis on Day 1, the k_{el} will only be reported if the $t_{1/2}$ of verproside or picroside II can be appropriately estimated from a 12-hour sampling period following dosing. In cases where the k_{el} interval is not assigned, the values of AUC_{0-inf} , $t_{1/2}$, CL/F , V_z/F , AUC_τ , CL_{ss}/F , V_{z_ss}/F , and $R_{A,AUC}$, as applicable, are considered not calculable and will not be reported. Wherever the resulting $t_{1/2}$ is more than half as long as the sampling interval, the k_{el} values and associated parameters (AUC_{0-inf} , $t_{1/2}$, CL/F , V_z/F , AUC_τ , CL_{ss}/F , V_{z_ss}/F , and $R_{A,AUC}$ as applicable) may not be presented as judged appropriate and in accordance with Celerion SOPs.

All available data will be included in the concentration and PK parameter tables to the extent possible. Patients will be excluded from the PK population if they significantly violate a protocol inclusion or exclusion criteria, deviate significantly from the protocol, or if data are unavailable or incomplete, which may influence the PK analysis.

Except if otherwise specified, available concentration and PK data of each patient will be included in the summary statistics and statistical comparisons for PK parameters.

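### The dose-normalised AUC0-t ratio in SAP Section 8.7 is pushed above 100% wherever samples fall below the assay limit before 12 h, by an amount the SAP cannot fix

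*SAP*

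**What the plan says.** Section 8.7 plans one comparison of exposure between the active doses, treatment B against treatment A, using three parameters from Day 54 (±1) or 56: AUCtau, AUC0-t and C_max_ss. It "will be performed by dose-normalized (to 80 mg YLP-001) ratio analysis" and reports a geometric mean ratio (GMR) with the "90% confidence interval (CI) of the GMR".

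The following passages decide what AUC0-t measures:

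- Section 8.5.1, Table 2, defines it as "AUC from time zero to time t , where t is the time of the" last measurable concentration. The AUCtau entry permits extrapolation to 12 h with kel when the last measurable concentration comes earlier; the AUC0-t entry has no such step.
- Section 8.2: the validated range "for verproside and picroside II is 50.0 – 20 000 pg/mL". One lower limit therefore serves both doses and both analytes.
- Section 8.5.1: "plasma concentrations BLQ after the first quantifiable concentration will be treated as missing", so the area ends at the last quantifiable sample.
- Section 8.5.1 also says, from half-lives seen at 80 mg BID in an earlier study in healthy subjects, that troughs "that are BLQ may be expected in this study".
- Section 8.5.1: AUCtau is not reported where kel cannot be assigned. AUC0-t needs no kel.

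For Day 1, Table 2 reports AUC0-t only if at least one patient falls below the limit before the last sample; otherwise AUC0-12 alone is given. Day 54/56 carries no such condition, and neither Section 8.7 nor the shells for Tables 11-13 and 14.2.4.1.8 add a caveat to the AUC0-t ratio.

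**The concern.** A dose-normalised ratio is read against 100%. That reading needs both arms to be integrated over the same interval, or over intervals whose difference does not depend on dose. AUC0-t fails this as soon as truncation occurs: with the same elimination, a patient on the higher dose stays above a fixed limit for longer.

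At stake is the only planned interval estimate of how exposure scales with dose. An AUC0-t ratio above 100% could be read as more than dose-proportional exposure at 160 mg when it only reflects the assay limit. Because both analytes share the limit, the same upward shift could appear in Tables 11-13 and 11-17 and look like corroboration. The AUC0-t row may also rest on more patients than the AUCtau row, since it survives where kel is not assigned, and so may attract more weight.

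**Working it through.** The SAP states no expected ratio, so there is no figure to reproduce.

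**Inputs from the SAP.** Lower limit L = 50 pg/mL (Section 8.2). Dose ratio 57.92/28.96 = 2.000, since "verproside content is 28.96 and 57.92 mg for the 80 and 160 mg YPL-001 dose levels, respectively" (Section 8.5.1). Sampling to 12 h, with gaps of 1 to 2 h after 4 h (Section 8.1.1). tmax about 0.75 h, because the 1.5 h emesis window is described as twice the estimated tmax (Section 8.5.1). 20 patients per arm (Section 3).

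**Assumed, because the SAP gives neither.** 80 mg Cmax of 100 to 10,000 pg/mL; half-life of 0.75 to 4 h.

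**Step 1, closed form.** Take C(t) = C0·exp(−kt) at 80 mg and exactly 2·C0·exp(−kt) at 160 mg, both crossing L before 12 h.

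- The crossing at 160 mg is later by ln2/k, one half-life.
- Area to the crossing: (C0 − L)/k at 80 mg and (2·C0 − L)/k at 160 mg. Halving the latter gives (C0 − L/2)/k.
- Ratio = (C0 − L/2)/(C0 − L), always above 1. With C0 = L·2^n this is (2^n − 0.5)/(2^n − 1): 116.7%, 107.1%, 103.3% and 101.6% for n = 2 to 5, and 100.8%, 100.4% and 100.2% for n = 6 to 8.

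If 160 mg is still measurable at 12 h and 80 mg is not, the ratio becomes (C0 − C12)/(C0 − L), where C12 is the 80 mg value at 12 h. Since L/2 ≤ C12 < L, it still exceeds 1 but is no larger than the value above. If both are measurable at 12 h, it is 100%.

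**Step 2, the SAP's grid and rules.** Exactly dose-proportional one-compartment steady-state profiles were sampled at the SAP times and integrated by linear trapezoid under the SAP's rules for values below the limit. The simulated GMR assumes a log-SD of 0.47 on Cmax (about 50% CV) and 0.3 on half-life, with typical half-lives of 1 to 3 h.

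| 80 mg Cmax (pg/mL) | Multiple of L | Closed form | Simulated GMR |
|---|---|---|---|
| 200 | 4 | 175/150 = 116.7% | 114–119% |
| 500 | 10 | 475/450 = 105.6% | 104.5–106.0% |
| 1,000 | 20 | 975/950 = 102.6% | 101.3–102.9% |
| 2,000 | 40 | 1975/1950 = 101.3% | 100.3–101.5% |
| 5,000 | 100 | 4975/4950 = 100.5% | 100.05–100.7% |
| 10,000 | 200 | 9975/9950 = 100.25% | not run |

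The GMR exceeded 100% in every simulated scenario. The mean delay in the last quantifiable sample was about 0.83–0.94 half-lives where nearly all patients fall below the limit before 12 h at both doses. It was much less where the 12 h cap applies (0.04 at half-life 3 h and Cmax 5,000).

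Single profiles vary. Half-life 2 h with Cmax 1,000 ends at 8 h against 10 h and gives 103.9%. Half-life 1.5 h with Cmax 500 ends at 6 h at both doses and gives exactly 100%.

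**Step 3, the other parameters.** AUCtau extrapolated to 12 h with the true kel on the same profiles gave 100.0–100.4% in nearly all cases (worst 104.7%, at a Cmax of only twice the limit). C_max_ss does not depend on where the curve is cut.

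**Step 4, precision for scale.** With 20 per arm, the interval around a true 100% is exp(±t(0.95, 38)·s·√(2/20)), with s = √ln(1 + CV²). This gives about 86–117% at an assumed CV of 30% and 78–129% at 50%.

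**The case against.** The best defence is about size and use. Cmax and half-life are not stated, and the validated range spans 400-fold (20,000/50). A Cmax of 128 times the limit (n = 7) gives only 100.4%, yet is compatible with troughs below the limit: 7 half-lives after 0.75 h fit inside 12 h for any half-life below (12 − 0.75)/7 ≈ 1.6 h. The SAP says only that such troughs may occur; it does not say in how many patients or how long before 12 h. The comparison serves an exploratory objective, has no acceptance bounds, and appears beside AUCtau and C_max_ss. t_last is to be reported for the same day, so truncation can be seen. All of this stands and keeps the point minor. It does not remove a bias of known direction.

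A reader might go further and infer that the 80 mg curve always stops a full half-life sooner. That is exact only in continuous time with both crossings before 12 h; on the SAP's grid the average shift is smaller, and some profiles show none.

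A reader might also infer that AUC0-t has no value at all. The SAP does not support that: where kel is not assigned, AUCtau is withheld and AUC0-t is the only full-profile area left for that patient. Simply deleting the row would confine the AUC comparison to patients with an assignable kel.

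**Conclusion.** The point holds as a conditional bias. If concentrations fall below 50 pg/mL before 12 h, which the SAP itself foresees, the expected dose-normalised AUC0-t ratio exceeds 100% under exact dose proportionality. The direction rests on linear kinetics and the same elimination at both doses.

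The size rests on an assumed 80 mg Cmax: from about 117% at 4 times the limit down to a negligible amount above 100 times. Claiming a shift of 5% or more as a finding about this trial would need a Cmax within about 10 times the limit, and nothing in the SAP establishes that. Against a 90% interval of roughly 78–129% at 50% CV, most of the range is hard to see. The other two parameters do not share the problem to any material degree, provided AUCtau is extrapolated whenever the last measurable concentration precedes 12 h. This is an inexpensive improvement to an exploratory analysis and does not threaten the trial's conclusions.

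**What to change.** - In Section 8.7, base the AUC dose comparison on AUCtau. State that extrapolation to 12 h is applied wherever it is needed and kel is assigned, instead of leaving it as something that may be done.
- Take AUC0-t out of the GMR and out of Tables 11-13, 11-17, 14.2.4.1.8 and 14.2.4.2.8. Keep it in the descriptive parameter tables, with t_last and N by arm.
- To retain patients without an assignable kel, replace the AUC0-t row with a partial AUC from 0 to one common nominal time per analyte, the same in both arms and chosen before unblinding by a written rule. An example is the latest nominal time at which a prespecified large majority of the pooled active-arm patients are quantifiable, with a stated rule for the few who are below the limit by then. Requiring every patient to be quantifiable would let one fast eliminator set the cut-off and discard valid data.

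Cost: SAP wording and one table row lost or replaced, with no new data. The partial AUC does not cover the full dosing interval, and its label should say so. If the sponsor keeps the AUC0-t ratio, the minimum is a footnote calling it supportive and dependent on the assay limit.

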9. PHARMACOKINETIC/PHARMACODYNAMIC RELATIONSHIP

There are no PK/PD analyses planned at this time. The PK/PD relationship(s) may be explored (e.g., graphically using scatter plots and an appropriate regression model), upon Sponsor's request.

10. SAFETY

No inferential statistics are to be performed for safety analysis.

The following are descriptions of the summary tables that will be created to assess safety. Table shells are also provided in Section 11. In the summary tables, N will be presented without decimal, minimum/maximum in same precision as in the database, mean/median in one more decimal than minimum/maximum, and SD in one more decimal than mean/median.

Where individual data points are missing because of dropouts or other reasons, the data will be summarized based on reduced denominators.

When change from baseline is calculated, baseline is the last schedule assessment before dosing, also including rechecks and unscheduled assessments, whichever is later. Rechecks, unscheduled assessments and early termination measurements taken after first dosing will not be used in the summarization.

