3. STUDY DESIGN

This is a Phase 2a, proof-of-concept, multicenter, randomized, double-blind, double-dummy, 3-treatment, parallel study, with low and high YPL-001 doses (80 mg and 160 mg twice daily [BID]) and a placebo control, in moderate to severe COPD male and female patients.

Sixty (60) patients will be enrolled and randomized into 3 treatment groups (20 patients per group). Patients will participate only once. An approximately equal number of current and ex-smokers will be enrolled in the study.

Screening of patients will occur within 14 days of Day 1 (inclusive) of the Run-in Period.

Following screening, eligible patients will discontinue non-permitted respiratory drugs and enter a 14 ± 2 days Run-in Period during which patients will be given albuterol taken on an as required basis and daily tiotropium 18 μ g to be administered at home. They will record their daily symptoms in an electronic diary (e-diary) throughout the Run-in Period.

Patients will return to the clinical research unit (CRU) in the morning of Day -3 to -1 for Check-in of the Treatment Period to confirm their eligibility and undergo Check-in scheduled study procedures. Patients will return to the CRU on the morning of Day 1 to be randomized and receive one of the 3 treatments and undergo all scheduled study procedures. Patients will return on the morning of Days 15 (± 2 days), 29 (± 2 days), 43 (± 2 days), 54 (± 1 day), and 56 of the Treatment Period for study drug administration and procedures. Prior to each release from the CRU, patients will receive sufficient doses to be self-administered at home until the next morning visit at the CRU. Patients will continue recording their daily symptoms via the e-diary throughout the Treatment Period.

YLP-001 and placebo will be administered approximately every 12 hours under fasting conditions.

Patients will remain ambulatory or seated upright for 1 hour following each study medication administration.

Safety and tolerability will be assessed throughout the study through physical examinations, vital signs, pulse oximetry, electrocardiograms (ECGs), clinical laboratory tests, and adverse events (AEs).

Assessment of respiratory symptoms and symptom burden in YPL-001 and placebo treatments will be performed daily through patient self-report of PEF, major and minor symptoms of COPD exacerbation, dyspnea, and activity.

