7.1.1.2 Biomarkers in Blood

Blood samples for PD assessments of biomarkers will be collected in pre-chilled evacuated tubes containing K₂EDTA at screening, on Days 1 and 54 (± 1) or Day 56 of the Treatment Period prior to dosing (predose) and at 1 hour postdose. In addition, predose samples will be collected on Days 15 (± 2), 29 (± 2), and 43 (± 2) of the Treatment Period.

Biomarker assessments include:

- WBC counts and differential (including monocytes, lymphocytes, neutrophils, and eosinophils) will be expressed as raw counts, % change from baseline, and as % of WBC for each differential.

WBC and differential counts in blood will be determined using a differential stain (blood smear; microscopic examination with manual differential WBC count) at the local Investigator sites.

- Concentrations of CRP, fibrinogen, TNF- α , IL-1 β , IL-4, IL-5, IL-6, IL-8, IL-13, MCP-1, and MMP-9 will be expressed as raw and % change from baseline levels. Baseline is defined as the predose time point at Check-in of the Treatment Period level and is patient specific.

The concentrations of MMP-9 will be determined using an ELISA assay and the rest of blood inflammatory markers will be determined using Luminex® assays. All assays are validated with respect to accuracy, precision, linearity, sensitivity,

and specificity at Temple University School of Medicine (Philadelphia, Pennsylvania, USA).

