10.1 Subject Discontinuation

Frequency counts will be tabulated by treatment and total for the number of subjects who were dosed, the number of subjects who completed, and the number of subjects who discontinued early, along with the reason for discontinuation. Individual patient's treatment along with their study completion status and date will be provided in a listing.

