10.5 Clinical Laboratory Tests (Serum Chemistry, Hematology, Urinalysis)

Clinical laboratory assessments (serum chemistry, hematology, and urinalysis) will be performed at screening, Check-in, Day 29 (± 2), and Day 55 or Day 56 or early termination.

Descriptive statistics (N, mean, SD, median, minimum, and maximum) will be reported for numeric clinical laboratory results and change-from-baseline values by treatment and time point of collection. Baseline value will be the Check-in value and is the last non-missing measurement prior to dosing. Postdose recheck values will not be used for calculation of descriptive statistics. Shift tables describing out-of-range shifts from baseline (in frequency counts) will be created. Out-of-normal-range and clinically significant laboratory values will be listed by patient. Early termination record will be excluded from the summary. All laboratory results will be listed in by-patient data listings. Because clinical laboratory test results will come from multiple sites with different reference ranges, out-of-range tables and shift tables will still use original units for presentation. For mean and mean change summary tables, the results and ranges will be converted to SI units for presentation. In the lab listings, both original units and SI units will be presented.

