10.6 Vital Signs and Pulse Oximetry

Vital signs include systolic and diastolic blood pressure, pulse rate, respiratory rate, and body temperature. They will be measured at screening, Check-in, predose and 1, 2, 6 hours postdose of Day 1, Days 15 (± 2), 29 (± 2), 43 (± 2), and predose and 1, 2, 6, 12 hours postdose of Day 55 or Day 56 or early termination. Pulse oximetry will be measured at screening, Check-in, and Day 55 or Day 56 or early termination. All vital signs and pulse oximetry results will be presented in a by-patient listing.

Descriptive statistics (N, mean, SD, median, minimum, and maximum) will be provided for vital sign variables and change from baseline at each assessment time point by treatment. Baseline value will be the Day 1 predose value and is the last observation, including rechecks, obtained prior to dosing. For pulse oximetry, baseline value will be the Check-in value and is the last observation, including rechecks, obtained prior to dosing. For the purposes of summary statistics calculations, recheck values will not be used in the determination of postdose values. Early termination record will be excluded from the summary.

10.7 12-lead Electrocardiogram

Twelve-lead ECGs will be performed at screening, Check-in, Day 29 (± 2), and Day 55 or Day 56 or early termination. All ECG results will be presented in a by-patient data listing.

Descriptive statistics (N, mean, SD, median, minimum, and maximum) will be provided for ECG variables (HR, PR, QRS, QT, and QTcB [Bazett's correction]) and

change from baseline at each assessment time point by treatment. Baseline value will be the Check-in value and is the last observation, including rechecks, obtained prior to dosing. For the purposes of summary statistics calculations, recheck values will not be used in the determination of postdose values. ECG results will also be classified as normal, abnormal, not clinically significant (ANCS), and abnormal, clinically significant (ACS). A normal-abnormal shift table will be created to describe shifts from predose baseline for postdose time points. Early termination record will be excluded from the summary.

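### Safety lab, SpO2 and ECG tables discard the planned early-termination values, so early stoppers can drop out of the post-dose comparison between arms

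*SAP*

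**What the plan says.** The general rule in section 10 is "Rechecks, unscheduled assessments and early termination measurements taken after first dosing will not be used in the summarization". Section 10.5 repeats it for laboratory tests, "Early termination record will be excluded from the summary", and sections 10.6 and 10.7 do the same for vital signs, pulse oximetry and ECG. The section 12.2 shells for Tables 14.3.5.1, .2 and .6 to .10 carry it as a footnote. Tables 14.3.5.3, .4 and .5 are built on those shells.

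The same sections schedule the measurement that is then set aside:

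- Laboratory tests (section 10.5): "will be performed at screening, Check-in, Day 29 (± 2), and Day 55 or Day 56 or early termination".
- Pulse oximetry (section 10.6): "Pulse oximetry will be measured at screening, Check-in, and Day 55 or Day 56 or early termination".
- ECG (section 10.7): "Twelve-lead ECGs will be performed at screening, Check-in, Day 29 (± 2), and Day 55 or Day 56 or early termination".

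Section 3 says what these data are for: "Safety and tolerability will be assessed throughout the study through physical examinations, vital signs, pulse oximetry, electrocardiograms (ECGs), clinical laboratory tests", together with adverse events. Section 2.1 makes safety and tolerability the primary objective. Section 4.1 keeps discontinued patients in the safety population for the time points at which they have data.

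**The concern.** The schedule treats early termination as the stand-in for the final visit, but the analysis rule removes what is collected there. Post-dose rechecks and unscheduled values are barred as well, so an early stopper has no other way into these rows. If a patient stops because of a laboratory, ECG or saturation problem, the value taken at stopping is the most informative one, and it is the one left out of the comparison by arm.

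Keeping such values out of the nominal-visit rows is sensible, because they do not belong to that visit. The fault is that no other row in the Section 14.3.5 laboratory, SpO2 and ECG tables uses them.

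**Working it through.** **Step 1. What remains once early-termination, recheck and unscheduled values are removed** (schedules from sections 7.1.1.2 and 10.5 to 10.7):

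| Measure | Post-dose times left | Stops before Day 29 visit | Stops after Day 29 visit, before Day 55/56 |
|---|---|---|---|
| SpO2 | Day 55/56 | none | none |
| Safety labs | Day 29, Day 55/56 | none | Day 29 only |
| ECG | Day 29, Day 55/56 | none | Day 29 only |
| Vital signs | Day 1 at 1, 2 and 6 h, then each visit attended | Day 1 and any later visit attended | Day 1 and later visits attended |

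Vital signs lose little. The pharmacodynamic blood markers are also not at issue. Besides Day 1 at 1 hour and the final visit predose and at 1 hour, section 7.1.1.2 says "In addition, predose samples will be collected on Days 15 (± 2), 29 (± 2), and 43 (± 2) of the Treatment Period". That makes 1 + 3 + 2 = 6 post-dose times, and a patient who stops before Day 29 still supplies one or two.

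**Step 2. How many patients.** The SAP gives 20 patients per arm (section 3) but no dropout rate and no attendance rate for the early-termination visit. Assume, for illustration only, k = 2 or 4 stoppers per arm (10–20%) and attendance a = 0.5 or 1. Collected SpO2 values left out of Table 14.3.5.8 = k × a:

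- k = 2: 1 (a = 0.5) or 2 (a = 1)
- k = 4: 2 (a = 0.5) or 4 (a = 1)

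**Step 3. Labs and ECG.** Assume stopping is spread evenly over 55 days. The share stopping before the Day 29 (±2) visit is 26/55 = 0.473, 28/55 = 0.509 or 30/55 = 0.545 for a visit on Day 27, 29 or 31. Multiplying by k × a:

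- k × a = 1: 0.47 to 0.55 patients per arm
- k × a = 2: 0.95 to 1.09
- k × a = 4: 1.89 to 2.18

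So about 0.5 to 2.2 of 20 per arm would have a collected lab or ECG value but no post-dose entry in those tables.

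**Step 4. Effect on the SpO2 mean.** Let the attending stoppers' mean change differ from the completers' by 1 point. A last-post-dose-value mean then differs from the Day 55/56 mean by k·a / (n − k + k·a), with n = 20:

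| k | a | Difference (points) |
|---|---|---|
| 2 | 0.5 | 1/19 = 0.053 |
| 2 | 1 | 2/20 = 0.100 |
| 4 | 0.5 | 2/18 = 0.111 |
| 4 | 1 | 4/20 = 0.200 |

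If stoppers and completers do not differ, only precision changes. In a shift table with 20 patients, each patient is 1/20 = 5 percentage points.

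**The case against.** The strongest reply is that the rule is deliberate, is stated the same way in text and shells, and is mostly harmless.

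- **The primary endpoint is untouched.** It is the number and severity of treatment-emergent adverse events, and no inferential safety analysis is planned. This stands, and it limits the point to descriptive comparison.
- **The information survives elsewhere.** Tables 14.3.4.1 to 14.3.4.3 show out-of-range laboratory values by patient with treatment. The 16.2.8 listings show all values, serious events have their own table and narratives are planned. Section 10.1 tabulates by arm "the number of subjects who discontinued early, along with the reason for discontinuation". This also stands. But by-patient displays are not a summary by arm, and SpO2 and ECG have no counterpart to Tables 14.3.4.1 to 14.3.4.3. The gap is widest for SpO2.
- **Section 4.1 defines a population, not the content of every table, and section 10 provides for reduced denominators.** The first half is fair, so the tension with section 4.1 is not a flat contradiction. Reduced denominators, however, answer for missing data, and these values are collected.
- **The size is assumed.** True; nothing in the SAP fixes it.
- **The added rows have weaknesses.** A last-value row mixes different lengths of exposure, and an any-post-baseline row gives patients sampled more often more chances of an abnormal result. Both need a footnote. Neither is a reason to omit the values altogether.

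**Conclusion.** The concern holds. By the schedule alone, without any assumption, an early stopper adds no post-dose SpO2 to Table 14.3.5.8. A stopper before the Day 29 visit adds nothing post-dose to the laboratory and ECG summary and shift tables. Later stoppers keep the visits they attended but lose the value at stopping.

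How many patients this touches cannot be read from the SAP. Under the assumed dropout and attendance it is 1 to 4 of 20 per arm for SpO2, and about 0.5 to 2.2 of 20 for labs and ECG if stopping is evenly spread. Bias, as opposed to lost precision, arises only if stopping is related to the measurement. The change should be made, but it does not threaten the primary endpoint.

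**What to change.** 1. Keep the by-visit rows on scheduled visits. Limit the exclusion wording in sections 10 and 10.5 to 10.7 and in the shell footnotes to those rows.
2. Add a row for the last post-dose value, including early termination, to Tables 14.3.5.1, .3, .5, .8 and .9.
3. Add an any-post-baseline row, including early-termination and unscheduled records, to shift Tables 14.3.5.2, .4, .6 and .10. Unscheduled records belong here because they too may be prompted by an abnormality. Count shifts to low and to high separately for chemistry and hematology, any out-of-range value for urinalysis, and the most abnormal of Normal/ANCS/ACS for ECG. State whether rechecks count.
4. Footnote both rows for variable timing and unequal sampling. A matching row in vital-sign Table 14.3.5.7 is optional.

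Two separate wording points can be settled in the same edit. The Table 14.3.5.7 shell promises an end-of-treatment presentation without defining it, and its footnote excludes early-termination records. The final-visit label in the laboratory, SpO2 and ECG shells is 54±2, whereas sections 10.5 to 10.7 say Day 55 or 56.

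The cost is SAP wording plus one row and one revised footnote in nine tables (5 summary + 4 shift). No new data are collected.
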